#### 2.1.4 Nonclinical Evaluation of EB-001

EB-001 has been evaluated in a series of pharmacology and non-clinical toxicology studies [REDACTED]

[REDACTED]

## 2.2 Rationale

### 2.2.1 Study Rationale

BoNT serotype E (BoNT/E) has been previously studied in human subjects with injection into the extensor digitorum brevis foot muscle ([Eleopra et al. 1998](#); [Eleopra et al. 2002](#)). These studies suggested a distinct clinical profile for BoNT/E versus the BoNT/A toxins, with faster onset and more limited duration of effect. IM administration of EB-001 bilaterally into pectoralis muscles during surgery has the potential to decrease post-operative focal musculoskeletal pain in the chest, including muscle spasm, pain and sensation of tightness. The efficacy is expected to start early in post-surgical period and is expected to last approximately 2-4 weeks.

Musculoskeletal pain is defined as pain originating from the skeletal muscles, tendons or ligaments due to focal injury in these structures. In subjects undergoing mammoplasty with sub-pectoral implant placement, the pectoralis major muscle is manipulated in order to form a sub-pectoral pocket for placement of the implant. Similarly, the RA muscle is stretched during plication in abdominoplasty. This manipulation of the RA muscles results in localized pain, muscular spasm, tenderness, and upper chest tightness or heaviness. Intramuscular injection of EB-001 is thought to reduce pain by relaxing the injured muscle, and by decreasing tension on the RA muscles and its tendons.

**Table 3      Likely Symptoms of Botulinum Toxin Poisoning or Overdose**

Body and Limbs Category	

Decreased muscle tone

Loss of muscle function

Loss of muscle tone

Weakened reflexes

Lack of reflexes

Muscular weakness

	

Muscle weakness of all four limbs

Partial loss of voluntary movement

Partial paralysis of one limb

Partial paralysis of one side of the body

Partial paralysis of the lower limbs

Pelvis muscle weakness

Brain Category	

Inability to send signals from your brain to your body

Interruption between brain and nerves in muscle

	
Eyes Category	

Abnormal pupil reflex

Blurred vision

Double vision

Drooping of upper eyelid

Eyelid function irregularity

Inability to focus or maintain a clear image

	

Partial loss of eye movement

Partial loss of eye muscle movement (eyelid)

Partial loss of eye muscle movement (vertical glaze)

Face Category	

Loss of facial movement

Loss of feeling in face

	

Loss of movement in face

Partial loss of feeling in face

Heart and Lungs Category	

Difficulty breathing

Inflammation of the lungs

Shortness of breath

	

Slowed breathing

Slow heart rate

Mouth Category	

Difficulty speaking

Difficulty swallowing

Difficulty with motor skills (slurred speech, difficulty chewing and swallowing)

Dry mouth

Inability to move vocal cords

	

Partial loss of facial motor functions (biting and chewing)

Partial loss of tongue movement

Speech impediment

Stuttering

Weakness of vocal cords

Stomach and Intestine Category	

Bowel blockage

Constipation

	

Unable to urinate completely

The safety evaluations in this protocol related to potential spread of toxin were based on the extensive knowledge about the systemic manifestations of botulism. It is well established that hematogenous spread of botulinum toxin leads to classic descending flaccid paralysis that starts with cranial nerve manifestations ([Sobel, 2005](#), [Gaware, 2011](#)) followed by symmetrical descending flaccid paralysis that may progress to respiratory compromise ([Sobel, 2005](#)). The earliest symptoms of botulism are typically diplopia and ptosis followed by facial or pharyngeal muscle paralysis progressing to upper and then lower extremity weakness, and finally appearance of respiratory symptoms due to diaphragm weakness. This classic progression of symptoms and signs suggests that SOT effects in the face would manifest before extremity weakness and respiratory symptoms. This is the basis for the focused neurological exam aimed at detecting SOT. In the event of systemic toxicity with EB-001, the muscle paralytic effect is expected to begin recovering approximately 1 week following dosing. In contrast, the muscle paralytic effect of Botulinum Toxin Type A is long, lasting up to several weeks to months.

Another risk is the possibility of an allergic reactions to drugs and to product ingredients. If a subject has a severe allergic reaction, death could occur. Likely signs or symptoms of allergic reactions (anaphylaxis) that could be life-threatening are:

- Rash
- Difficulty in breathing or inability to breathe without assistance
- Wheezing
- Sudden drop in blood pressure (dizziness)
- Swelling around the mouth, throat, or eyes
- Fast pulse
- Sweating
- Feeling of dread

Documented events of serious allergic reactions have been rare in the case of botulinum neurotoxin serotype A (for example, see [Botox® Cosmetic Label](#)).

Localized pain, infection, inflammation, tenderness, swelling, erythema, and/or bleeding/bruising may be associated with the injection.

### **2.3.2 Known Potential Benefits**

Potential benefits to subjects in this study may be decreased pain following abdominoplasty and a decrease in the use of opioid medications post-surgery.

## **3 OBJECTIVES AND PURPOSE**

This study will evaluate the safety and efficacy of EB-001 in decreasing the post-surgical pain in patients undergoing elective abdominoplasty surgery.

The safety objective is to determine the safety and tolerability of a single intraoperative

treatment of EB-001 IM injections into the RA muscles in subjects undergoing elective abdominoplasty surgery.

The efficacy objective is to evaluate the efficacy of intraoperative administration of EB-001 IM into the RA muscles in reducing the pain and use of rescue pain medications in subjects undergoing elective abdominoplasty surgery.

## 4 STUDY DESIGN AND ENDPOINTS

### 4.1 Description of the Study Design

This will be a two-stage study. The study will be conducted at up to two surgical centers that specialize in elective abdominoplasty surgeries and enroll up to 39-57 subjects in Stage 1 and 66 subjects in Stage 2 ([Figure 1](#)), with up to 67-82 subjects exposed to active drug. The study will include a screening visit to determine subject eligibility. On the day of surgery, subjects will be admitted to an inpatient clinic for 5 days post-operatively (Days 1-5) ([Table 1](#) and [Table 2](#)). Intraoperatively, a single dose of EB-001 IM will be given via IM injections into the RA muscles per the surgical procedure manual. Follow up visits will be scheduled at days 8, 15, and 29.

The first stage will be a placebo controlled, single-blind (to subject and staff at study sites), single ascending cohort study stratified by ethnicity (Hispanic and non-Hispanic) starting from Cohort 2. Six cohorts (3-8 subjects per cohort) will be dosed at 6 ascending doses of EB-001. An optional Cohort 7 may be considered.

Cohort 1 sentinel group (3 subjects; 1 active: 2 placebo) [REDACTED] The rest of the cohort (5 subjects; 3 active: 2 placebo) will be dosed at the same dose after review of all available data by the Safety Review Committee (SRC) is conducted, with safety data through at least Day 5 post-operatively.

Cohort 2 sentinel group (3 subjects; 1 active: 2 placebo) [REDACTED] after review of all available safety data from the prior cohort through at least Day 5 post-operatively. The rest of the cohort (5 subjects; 3 active: 2 placebo) will be dosed after review of all available data by the SRC is conducted, with safety data through at least Day 5 post-operatively.

Cohort 3 sentinel group (3 subjects; 1 active: 2 placebo) [REDACTED] after review of all available safety data from the prior cohorts through at least Day 5 post-operatively. The rest of the cohort (5 subjects; 3 active: 2 placebo) will be dosed after review of all available data by the SRC is conducted, with safety data through at least Day 5 post-operatively.

Cohort 4 group (5 subjects; 4 active: 1 placebo) [REDACTED] after review of all available safety data from the prior cohort through at least Day 5 post-operatively.

Cohort 5 group (3 subjects; 2 active: 1 placebo) [REDACTED] after review of all available safety data from the prior cohort through at least Day 5 post-operatively.

Cohort 6 sentinel group (2 subjects; 1 active: 1 placebo) [REDACTED] after review of all available safety data from the prior cohorts through at least Day 5 post-operatively. The rest of the cohort (6 subjects; 5 active: 1 placebo) will be dosed after review of all available data by the SRC is conducted, with safety data through at least Day 5 post-operatively.

Optional Cohort 7 (up to 18 subjects; 15 active: 3 placebo) will be dosed at a dose previously assessed after review of all available safety data from the prior cohorts through at least Day 5 post-operatively.

In the event an intolerable dose is identified, a lower (intermediary) dose may be evaluated as proposed by the SRC. This lower dose may be a repeat of the prior lower dose cohort or an intermediary dose between the intolerable dose and prior lower dose cohort. See further details in [Flexibility in Dose Adjustment of Stage 1](#).

The second stage will be a randomized, placebo-controlled, double blind, parallel 3-arm study. In this stage, there will be 2 doses of EB-001 (to be determined by the SRC after last dosing of last subject of Stage 1) and placebo in a 1:1:1 ratio for a total of 66 subjects stratified by ethnicity (Hispanic and non-Hispanic). SRC will meet periodically to review safety data.

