**Study Design:**

This will be a two-stage study. The study will be conducted at up to two surgical centers that specialize in elective abdominoplasty surgeries. The study will include a screening visit to determine subject eligibility. On the day of surgery, subjects will be admitted to an inpatient clinic for 5 days post-operatively (Days 1-5) (Table 1 and Table 2). Intraoperatively, a single dose of EB-001 IM will be given via IM injections into each RA muscles per the surgical procedure manual. Follow up visits will be scheduled at days 8, 15, and 29.

The first stage will be a placebo-controlled, double blinded (to subject, investigator, and site staff), single ascending dose cohort study. The study is stratified by ethnicity (Hispanic and non-Hispanic) starting from Cohort 2. Six cohorts (3-8 subjects per cohort) will be dosed at 6 ascending doses of EB-001. An optional Cohort 7 may be considered. Clinical staff at the sponsor will be unblinded to drug assignment.

[REDACTED]

[REDACTED]

[REDACTED]

[REDACTED]

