**Flexibility in Dose Adjustment of Stage 1:**

In the first stage of the study, if an intolerable dose is identified (based on one of the above 5 criteria), a lower dose may be evaluated as proposed by the SRC. This lower dose may be a repeat of the prior lower dose cohort or an intermediary dose between the intolerable dose and prior lower dose cohort. If the dose is an intermediary dose, a sentinel group consisting of 2 subjects (1 active: 1 placebo) will be dosed first. The SRC will review all available safety data of the prior sentinel group through at least Day 5 post-operatively, and 6 additional subjects (5 active: 1 placebo) will be dosed upon approval.

In addition, if the SRC deems appropriate, before an intolerable dose is identified, a repeat dose, or a dose not exceeding the planned dose of the next cohort may be evaluated.

If a repeat or lower dose (i.e., any dose at or lower than prior highest dose evaluated without meeting stopping criteria) is considered, subjects may be dosed without implementing sentinel dosing strategy.

All dose escalation/adjustments or additional cohorts and corresponding sample size will be determined by the SRC. [REDACTED]

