**Table 4      Toxicity Criteria**

TEAE	Definition 
Serious adverse event	See Section 8.1.2
TEAEs related to spread of toxin, including PFTs	SOT: FDA Draft Guidance: Upper Facial Lines: Developing Botulinum Toxin Drug Products  $\geq$ Grade 2 SVC: SVC on PFT with a reduction of greater than 40% relative to baseline pre-dose measure and the absolute SVC less than 2 L at 96 hours (Day 5) post-dose or later, when confirmed by a repeat SVC approximately 4 hours later.
Post-operative TEAEs of Special Interest	Tachypnea, tachycardia, and fever according to the Guidance for Vaccine Trials in Healthy Volunteers  $\geq$ Grade 2 Pneumonia or atelectasis diagnosed clinically and confirmed by chest x-ray Dyspnea with a clinical diagnosis of moderate or worse severity
TEAEs related to Laboratory and ECG parameters 	Guidance for Vaccine Trials in Healthy Volunteers  $\geq$ Grade 2
All others TEAEs (other than the SOT, post-operative TEAEs of Special Interest, or laboratory and ECG parameters)	Guidance for Vaccine Trials in Healthy Volunteers  $\geq$ Grade 3

 Unless considered to be unrelated to study medication

 FDA Draft Guidance, Upper Facial Lines: Developing Botulinum Toxin Drug Products ([FDA 2014](#)).

 Guidance for Industry: Toxicity Grading Scale for Health Adult and Adolescent Volunteers Enrolled in Preventive Vaccine Clinical Trials ([FDA 2007](#))

 To be confirmed by a repeat test

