**Flexibility in Dose Adjustment of Stage 1:**

[figure not shown]
In the first stage of the study, if an intolerable dose is identified (based on one of the above 5 criteria), a lower dose may be evaluated as proposed by the SRC. This lower dose may be a repeat of the prior lower dose cohort or an intermediary dose between the intolerable dose and prior lower dose cohort. If the dose is an intermediary dose, a sentinel group consisting of 2 subjects (1 active: 1 placebo) will be dosed first. The SRC will review all available safety

data of the prior sentinel group through at least Day 5 post-operatively, and 6 additional subjects (5 active: 1 placebo) will be dosed upon approval.

In addition, if the SRC deems appropriate, before an intolerable dose is identified, a repeat dose, or a dose not exceeding the planned dose of the next cohort may be evaluated.

If a repeat or lower dose (i.e., any dose at or lower than prior highest dose evaluated without meeting stopping criteria) is considered, subjects may be dosed without implementing sentinel dosing strategy.

All dose escalation/adjustments or additional cohorts and corresponding sample size will be determined by the SRC. [REDACTED]

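### Cohorts 4 and 5 are listed as new ascending doses but show no sentinel step; holding Cohort 4 after two subjects would reduce the larger exposure at little cost

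*Protocol*

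**What the plan says.** The Protocol Summary (Study Design) and Section 4.1 both state the escalation plan: "Six cohorts (3-8 subjects per cohort) will be dosed at 6 ascending doses of EB-001".

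Where a sentinel is used, Section 4.1 describes it in two steps. An example of the first step is "Cohort 3 sentinel group (3 subjects; 1 active: 2 placebo"; the remaining five subjects (3 active, 2 placebo) wait for an SRC review that includes safety data to Day 5 or later. Cohorts 1 and 2 have the same structure. Cohort 6 has a smaller first step, "Cohort 6 sentinel group (2 subjects; 1 active: 1 placebo", and then six more subjects (5 active, 1 placebo) after the same kind of review.

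Cohort 4 has one step: "Cohort 4 group (5 subjects; 4 active: 1 placebo". Cohort 5 is also one step, with 3 subjects (2 active, 1 placebo). Each opens after review of the cohort before it, and neither entry mentions a remainder. Section 10.6.1 agrees: it gives separate sentinel ratios for Cohorts 1-3 and 6, and only an overall ratio for Cohorts 4 (4:1) and 5 (2:1).

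The text on flexibility in Stage 1 dosing says when a sentinel is needed for SRC adjustments: "If the dose is an intermediary dose, a sentinel group consisting of 2 subjects (1 active: 1 placebo) will be dosed first". It waives sentinel dosing for a repeat or lower dose, explained as "any dose at or lower than prior highest dose evaluated without meeting stopping criteria".

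**The concern.** A sentinel limits how many people receive an untested dose before anyone has looked at that dose. Cohorts 4 and 5 are described as higher than everything before them, so on the visible text they fall outside the stated waiver. Their only planned gate is a review of a lower dose. The first planned Day 5 review at the Cohort 4 dose is the one that opens Cohort 5, and the first at the Cohort 5 dose is the one that opens Cohort 6. Those reviews protect the next cohort and come too late for the one being reviewed.

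What is at stake is mainly late signals. The slow vital capacity (SVC) criterion in Table 4 needs a fall of more than 40% from baseline together with "the absolute SVC less than 2 L at 96 hours (Day 5) post-dose or later", confirmed by a repeat about 4 hours later. If Cohort 4 surgeries were scheduled close together, all four active subjects could be dosed before any of them could have met it.

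**Working it through.** **Inputs.** Cohort sizes and splits come from Protocol Section 4.1. Stage 1 totals come from Section 10.5.

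**Check that the cohort structure has been read correctly.** Cohorts 1-6, active: 3 × 4 + 4 + 2 + 6 = 24. Placebo: 3 × 4 + 1 + 1 + 2 = 16. Total: 40. Adding optional Cohort 7 (15 active, 3 placebo) gives 39 + 19 = 58. These match the 40-58 (24-39 active, 16-19 placebo) in Section 10.5, so a Cohort 4 of 5 with 4 active is what the plan counts. Section 4.1 itself states 39-57, one lower at each end; that does not bear on this point.

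**Active subjects dosed before the first planned Day 5 SRC review at their own dose.**

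| Dose level | Before review | Active in cohort | Share |
|---|---|---|---|
| Cohorts 1, 2, 3 (each) | 1 | 1 + 3 = 4 | 25% |
| Cohort 4 | up to 4 | 4 | up to 100% |
| Cohort 5 | up to 2 | 2 | up to 100% |
| Cohort 6 | 1 | 1 + 5 = 6 | 17% |

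Optional Cohort 7 is left out because it uses a dose already assessed, so the waiver applies.

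**Effect of a hold after two subjects in Cohort 4**, assuming the five are in random order:

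- Both active: C(4,2)/C(5,2) = 6/10 = 60%.
- One active and one placebo: 4/10 = 40%.
- No active subject: impossible, since there is only one placebo.
- Mean active before review: 0.6 × 2 + 0.4 × 1 = 1.6. Mean active held back: 4 − 1.6 = 2.4.

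Stratification by ethnicity could shift the 60/40 split, but the bounds of 1 and 2 stay.

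**Effect on the blind.** With a fixed 1:1 sentinel ratio the only placebo would be used in the first two, and anyone who knew the ratio would know that the last three were active. Without a fixed ratio, the placebo lies among the last three with probability 3/5, so each has a (3/5)/3 = 1/5 chance of placebo, the same as at the start.

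No number of averted events is given. It would need a toxicity rate, an enrollment rate and an SRC stopping rule, and the visible documents state none of them.

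**The case against.** The strongest objection is that the deciding information is hidden. Amendment 4 revised the dosing rationale, regimen and sample size after FDA feedback. Its account of the added cohorts is redacted, as is part of the Cohort 4 sentence. Having no sentinel at Cohorts 4 and 5 and one again at Cohort 6 could be a deliberate choice tied to the size of each dose step. This stands and limits confidence. A hidden sentinel is less likely: Section 10.6.1 is readable and gives none for Cohorts 4 or 5. That section lists ratios and not dosing intervals, however, so it cannot exclude a timed stagger described elsewhere.

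Several stronger readings are tempting, and the documents do not support them.

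- *Cohort 4 is the only exception.* It is not; Cohort 5 has the same gap. Cohort 5's three subjects equal the sentinel groups of Cohorts 1-3 in total, but those groups hold one active subject and Cohort 5 holds two. Reliance on the prior cohort's review does not single out Cohort 4 either, since Cohorts 2 and 5 have the same gate.
- *The protocol breaks its own rule.* The intermediary-dose text governs SRC adjustments once an intolerable dose has been found, when toxicity has already been seen just above. For planned escalation it is only a loose benchmark.
- *Nothing could be detected before Day 5.* That is true of the SVC criterion alone. The protocol's risk section expects that "SOT effects in the face would manifest before extremity weakness and respiratory symptoms". Other toxicity criteria, the stay through Day 5 and continuous safety monitoring can all act sooner.
- *The sentinel was dropped by mistake.* SAP Section 2.4.3 lists one for a then-optional Cohort 4, but the SAP is based on Amendment 3. That text is superseded and the dose may differ.

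It is also fair to object that a two-subject hold does not reproduce a one-active sentinel: 60% of the time both subjects are active. That is the price of keeping the blind with one placebo in the cohort.

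**Conclusion.** The point holds as an inconsistency in the visible plan. Two dose levels described as new and higher, Cohorts 4 and 5, lack the within-cohort review given to Cohorts 1-3 and 6. Cohort 4 is the larger exposure: up to 4 active subjects before an at-dose Day 5 review, against 2 in Cohort 5 and 1 elsewhere.

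This rests on taking the six ascending doses at face value and on no stagger being stated in redacted text. The documents do not show that the omission was unjustified, or that the dose step was large.

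It had no consequence in the trial: SAP Section 2.4.3 records that enrollment was put on hold after Cohort 3 and the study later terminated, so no Cohort 4 subject was dosed. The value lies in the plan as written and in any reuse of it. It is a cheap improvement worth making, with medium confidence.

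**What to change.** In the Protocol Summary and Sections 4.1 and 10.6.1, state that the first two Cohort 4 subjects are dosed from the existing 4:1 allocation with no set sentinel ratio, and that the other three wait for SRC review with data through at least Day 5. Two subjects is the sentinel size already used for Cohort 6 and for intermediary doses. Cohort 5 may stay as written, because its 2 active subjects equal the most that the revised Cohort 4 would expose before review.

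If Cohort 4 is in fact not above the highest dose already evaluated without meeting stopping criteria, correct the statement of six ascending doses instead and cite the waiver.

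The cost is amendment wording and about one review interval (96 hours plus SRC turnaround) in one cohort. Sample size and allocation do not change, and the blind is kept.

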**Investigational (Study) Sites:**

It is expected that up to 2 clinical surgical sites will conduct the study and enroll approximately 105-123 subjects.

[REDACTED]

[REDACTED]

[REDACTED]

[figure not shown]
**Placebo:**

**Dosage:**

The total dose of active drug will be the specified amount of EB-001 [REDACTED] [REDACTED]. Each dose will be administered into the RA muscles per instructions in the surgical procedure manual. The injection paradigm will be the same for each cohort.

Study drug injections will be performed intraoperatively under general anesthesia, under direct visualization of the RA muscles. Intramuscular needle placement, types of needles used, and additional instructions for study drug administration are referenced in the study

manual(s).

**Table 4      Toxicity Criteria**

TEAE	Definition 
Serious adverse event	See Section 8.1.2
TEAEs related to spread of toxin, including PFTs	SOT: FDA Draft Guidance: Upper Facial Lines: Developing Botulinum Toxin Drug Products  $\geq$ Grade 2 SVC: SVC on PFT with a reduction of greater than 40% relative to baseline pre-dose measure and the absolute SVC less than 2 L at 96 hours (Day 5) post-dose or later, when confirmed by a repeat SVC approximately 4 hours later.
Post-operative TEAEs of Special Interest	Tachypnea, tachycardia, and fever according to the Guidance for Vaccine Trials in Healthy Volunteers  $\geq$ Grade 2 Pneumonia or atelectasis diagnosed clinically and confirmed by chest x-ray Dyspnea with a clinical diagnosis of moderate or worse severity
TEAEs related to Laboratory and ECG parameters 	Guidance for Vaccine Trials in Healthy Volunteers  $\geq$ Grade 2
All others TEAEs (other than the SOT, post-operative TEAEs of Special Interest, or laboratory and ECG parameters)	Guidance for Vaccine Trials in Healthy Volunteers  $\geq$ Grade 3

 Unless considered to be unrelated to study medication

 FDA Draft Guidance, Upper Facial Lines: Developing Botulinum Toxin Drug Products ([FDA 2014](#)).

 Guidance for Industry: Toxicity Grading Scale for Health Adult and Adolescent Volunteers Enrolled in Preventive Vaccine Clinical Trials ([FDA 2007](#))

 To be confirmed by a repeat test

